9.4.7 Treatment Compliance

Records of treatment compliance for each subject will be kept during the study. The CRAs will review treatment compliance during site visits and at the completion of the study.

Per visit schedule, subjects will return unused study drug and be given a new supply; pill counts will be made by study staff on returned medication.

9.4.8 Drug Supplies and Accountability

In compliance with local regulatory requirements, drug supplies will not be sent to the investigator until the following documentation has been received by the sponsor:

- A signed and dated confidentiality agreement
- A copy of the final protocol signature page, signed and dated by both the sponsor and investigator
- Written proof of approval of the protocol, the ICFs, and any other information provided to the subjects by the IRB/IEC for the institution where the study is to be conducted
- A copy of the IRB/IEC-approved ICF and any other documentation provided to the subjects to be used in this study
- The IRB/IEC membership list and statutes or Health and Human Services Assurance number
- A copy of the certification and a table of the normal laboratory ranges for the reference laboratory conducting the clinical laboratory tests required by this protocol
- An investigator-signed and dated Form FDA 1572, where applicable
- Financial Disclosure form(s) for the PI and all sub-investigators listed on Form FDA 1572, where applicable
- A signed and dated curriculum vitae of the PI including a copy of the PI's current medical license or medical registration number on the curriculum vitae
- A signed and dated clinical studies agreement
- A copy of the current Controlled Substance Registration Certificate-Form DEA 223 (US sites only). Must be appropriate to handle schedule IV products and not be expired.

The investigational product can only be shipped to the exact address detailed on the site's form DEA 223. If a site requires drug to be shipped to a particular location, then an appropriate form DEA 223 certificate must be provided for that location.

The investigator and the study staff will be responsible for the accountability of all study drugs/study supplies (dispensing, inventory, and record keeping) following the sponsor's instructions and adherence to GCP guidelines as well as local or regional requirements.

Under no circumstances will the investigator allow the study drugs/study supplies to be used other than as directed by this protocol. Study drugs/study supplies will not be dispensed to any individual who is not enrolled in the study.

The site must maintain an accurate and timely record of the following: receipt of all study drugs/study supplies, dispensing of study drugs/study supplies to the subject, collection and reconciliation of unused study drugs/study supplies that are either returned by the subjects or

shipped to site but not dispensed to subjects, and return of reconciled study drugs/study supplies to the sponsor or (where applicable) destruction of reconciled study drugs/study supplies at the site. This includes, but may not be limited to: (a) documentation of receipt of study drugs/study supplies, (b) study drugs/study supplies dispensing/return reconciliation log, (c) study drugs/study supplies accountability log, (d) all shipping service receipts, (e) documentation of returns to the sponsor, and (f) certificates of destruction for any destruction of study drugs/study supplies that occurs at the site. All forms will be provided by the sponsor. Any comparable forms that the site wishes to use must be approved by the sponsor.

The study drugs/study supplies and inventory records must be made available, upon request, for inspection by a designated representative of the sponsor or a representative of a health authority (eg, FDA, Medicine and Healthcare Products Regulatory Agency). As applicable, all unused study drugs/study supplies and empty and partially empty containers from used study drugs/study supplies are to be returned to the investigator by the subject and together with unused study drugs/study supplies that were shipped to the site but not dispensed to subjects are to be returned to the sponsor's designated central or local depot(s) during the study or at the conclusion of the study, unless provision is made by the sponsor for destruction of study drugs/study supplies and containers at the site. Destruction at the site will only occur under circumstances where regulation or supply type prohibits the return of study drugs/study supplies to the central or local depot(s). Approval for destruction to occur at the site must be provided by the sponsor in advance. Upon completion of drug accountability and reconciliation procedures by the site's personnel and documentation procedures by the sponsor's personnel, study drugs/study supplies that are to be returned to the sponsor's designated central or local depot(s) must be boxed and sealed and shipped back to the central or local depot(s) following all local regulatory requirements. In some regions, study drugs/study supplies may be removed from the site and hand delivered to the central or local depot by sponsor representatives. Where study drugs/study supplies are approved for destruction at the site, destruction will occur following the site's standard procedures and certificates of destruction will be provided to the sponsor.

Drug accountability will be reviewed during site visits and at the completion of the study.

9.5 Study Assessments

9.5.1 Assessments

9.5.1.1 Demography

Subject demography information will be collected at the first visit. Demography information includes date of birth (or age), sex, and race/ethnicity.

9.5.1.2 Baseline Assessments

9.5.1.2.1 MEDICAL HISTORY

Medical and surgical history and current medical conditions will be recorded at the first visit. All medical and surgical history within 5 years must be noted in the Medical History and Current Medical Conditions CRF.

9.5.1.3 Efficacy Assessments

- Body weight and height will be measured using a standard stadiometer method ([Lohman T, et al, 1988](#)) to calculate changes in BMI; BMI will then be used to calculate the proportion (%) of patients achieving at least a 5% and at least a 10% BMI reduction.
- Measurement of systolic and diastolic BP, heart rate, fasting lipids (total cholesterol, HDL cholesterol, LDL cholesterol, and triglycerides), fasting plasma glucose, fasting insulin, hemoglobin A_{1c} (HbA_{1c}), and HOMA-IR to assess changes in cardiovascular and metabolic risk profiles from Baseline to Week 52
 - Prehypertension and primary hypertension as defined by the Expert Panel on Integrated Guidelines for Cardiovascular Health and Risk Reduction in Children and Adolescents ([Expert Panel on Integrated Guidelines for Cardiovascular Health and Risk Reduction in Children and Adolescents, 2011](#))
 - Dyslipidemia as defined by the Expert Panel on Integrated Guidelines for Cardiovascular Health and Risk Reduction in Children and Adolescents ([Expert Panel on Integrated Guidelines for Cardiovascular Health and Risk Reduction in Children and Adolescents, 2011](#))

9.5.1.4 Pharmacokinetic, Pharmacodynamic, Pharmacogenomic, and Other Biomarker Assessments

9.5.1.4.1 PHARMACOKINETIC ASSESSMENTS

Blood samples (approximately 4 mL each) for PK assessments will be collected at Weeks 12, 28, 36, and 52 for population PK analyses. All subjects will be instructed to take their study drug in the morning on the day before their scheduled clinic visit at Weeks 12, 28, 36, and 52. No additional doses should be taken that day for those subjects who have been taking their doses in the evening. Dose times **must** be recorded for the last 2 dosing times prior to the clinic visit.

On the day of the Week 12, 28, and 52 clinic visits, subjects will be instructed to take their study drug at approximately the same time as the morning before, with no additional doses taken that day. Two blood samples for determination of plasma concentrations of lorcaserin will be taken at each of these visits: within 30 minutes before dosing and within 1 to 3 hours after dosing.

On the day of the Week 36 clinic visit, subjects will take their study drug at home in the morning in the morning **at home**. One blood sample for determination of plasma concentration of lorcaserin will be collected at the clinic within 4 to 6 hours after dosing.

Plasma lorcaserin concentrations will be measured using a validated liquid chromatography method coupled with tandem mass spectrometry method. The collection, handling, and shipping procedures for PK samples will be described in a manual to be provided to the study sites.

9.5.1.4.2 PHARMACODYNAMIC ASSESSMENTS

Blood samples will be collected to determine lorcaserin plasma exposure and population PK/PD modeling will be used to explore the relationship between lorcaserin plasma exposure and following response to lorcaserin:

- Change from Baseline in BMI
- Proportion (%) of patients achieving at least a 5% and at least a 10% reduction in BMI

Other PD endpoints will be considered based on the data at the end of the study to explore their relationships with lorcaserin plasma exposure.

9.5.1.4.3 PHARMACOGENOMIC AND OTHER BIOMARKER ASSESSMENTS

Not applicable

9.5.1.5 Safety Assessments

Safety assessments will consist of monitoring and recording all AEs and serious adverse events (SAEs); electrocardiograms (ECGs); laboratory evaluations for hematology, metabolic function (glucose, lipids, and thyroid), adrenal functions, and biochemical blood and urine bone health assessments; blood chemistry and urine values; neuropsychiatric events; periodic measurements of vital signs, neuromuscular signs for screening potential serotonin syndrome, and signs and symptoms of priapism and prolactinemia; and performance of physical examinations. In subjects with potential prolactin-related AEs, such galactorrhea, changes in libido, or changes to menstrual cycle, prolactin level will be measured and assessed. Study drug effect on growth of adolescents will be evaluated using the CDC growth chart at Baseline, and Weeks 5, 12, 28, 36, 52, and at Follow-Up; a full physical examination at Baseline, Weeks 12, 28, 52, and at Follow-Up; and bone age determination by x-ray of the hand at Baseline, Weeks 12, 28, and 52. Sexual maturation will be evaluated by assessing sex hormones and self-reported changes in Tanner Staging at Baseline, Weeks 28 and 52, and at Follow-Up.

The C-SSRS will be used to assess all subjects in the study for any signal of depression or suicidal ideation or behavior. Additionally, screening, diagnosing, monitoring, and measuring the severity of depression will be assessed using the PHQ-9 and effects on cognitive function will be assessed using WRAML-2.

Echocardiographic assessments will be used to exclude subjects with FDA-defined valvulopathy, pulmonary hypertension, and other major cardiovascular disease (as outlined in Exclusion Criterion No. 3) during the Screening Period. Additionally, cardiac valvular function and pulmonary systolic pressure changes at Weeks 28 and 52 will be assessed. Valvular regurgitation as assessed in the echocardiogram will be rated absent, trace, mild, moderate, or severe for the aortic, mitral, and tricuspid valves; the rating will be absent or present for the pulmonic valve. The evaluations will be based on guidelines from the American Society of Echocardiography. Pulmonary artery pressure will be estimated from the tricuspid regurgitant jet velocity.

9.5.1.5.1 ADVERSE EVENTS AND EVENTS ASSOCIATED WITH SPECIAL SITUATIONS

An AE is any untoward medical occurrence in a patient or clinical investigation subject administered an investigational product. An AE does not necessarily have a causal relationship with the medicinal product. For this study, the study drug is Belviiq XR (lorcaserin hydrochloride).

The criteria for identifying AEs in this study are:

- Any unfavorable and unintended sign (including an abnormal laboratory finding), symptom, or disease temporally associated with the use of an investigational product, whether or not considered related to the investigational product (Note: Every sign or symptom should not be listed as a separate AE if the applicable disease [diagnosis] is being reported as an AE)
- Any new disease or exacerbation of an existing disease
- Any deterioration in non-protocol-required measurements of a laboratory value or other clinical test (eg, ECG, x-ray) that results in symptoms, a change in treatment, or discontinuation of study drug
- Recurrence of an intermittent medical condition (eg, headache) not present pretreatment (Baseline)
- An abnormal laboratory test result should be considered an AE if the identified laboratory abnormality leads to any type of intervention, withdrawal of study drug, or withholding of study drug, whether prescribed in the protocol or not.

All AEs observed during the study will be reported on the Adverse Event CRF. All AEs, regardless of relationship to study drug or procedure, should be collected beginning from the time the subject signs the study ICF through the last visit in the Treatment Phase. Subjects who fail screening primarily due to AE(s) must have the AE(s) leading to screen failure reported on the Screening Disposition CRF. SAEs will be collected for 28 days after the last dose.

Abnormal laboratory values should not be listed as separate AEs if they are considered to be part of the clinical syndrome that is being reported as an AE. It is the responsibility of the investigator to review all laboratory findings in all subjects and determine if they constitute an AE. Medical and scientific judgment should be exercised in deciding whether an isolated

laboratory abnormality should be classified as an AE. Any laboratory abnormality considered to constitute an AE should be reported on the Adverse Event CRF.

Abnormal ECG (corrected QT interval [QTc]) results, if not otherwise considered part of a clinical symptom that is being reported as an AE, should be considered an AE if the QTc interval is greater than 450 msec and there is an increase of more than 60 msec from baseline. Any ECG abnormality that the investigator considers as an AE should be reported as such.

It is the responsibility of the investigator to review the results of the C-SSRS, PHQ-9, and WRAML-2 in all subjects and determine if any result constitutes an AE. Medical and scientific judgment should be exercised in deciding whether an isolated suicidality rating scale response should be classified as an AE (see [Section 9.5.1.5.9](#) for a description of the C-SSRS).

All AEs must be followed for 28 days after the subject's last dose or until resolution, whichever comes first. All SAEs must be followed to resolution or, if resolution is unlikely, to stabilization.

Every effort must be made by the investigator to categorize each AE according to its severity and its relationship to the study treatment.

Assessing Severity of Adverse Events

Adverse events will be graded on a 3-point scale (mild, moderate, severe) and reported in the detail indicated on the CRF. The definitions are as follows:

Mild Discomfort noticed, but no disruption of normal daily activity

Moderate Discomfort sufficient to reduce or affect normal daily activity

Severe Incapacitating, with inability to work or to perform normal daily activity

The criteria for assessing severity are different than those used for seriousness (see [Section 9.5.1.5.2](#) for the definition of an SAE).

Assessing Relationship to Study Treatment

Items to be considered when assessing the relationship of an AE to the study treatment are:

- Temporal relationship of the onset of the event to the initiation of the study treatment
- The course of the event, especially the effect of discontinuation of study treatment or reintroduction of study treatment, as applicable
- Whether the event is known to be associated with the study treatment or with other similar treatments
- The presence of risk factors in the study subject known to increase the occurrence of the event

- The presence of nonstudy, treatment-related factors that are known to be associated with the occurrence of the event

Classification of Causality

The relationship of each AE to the study drug will be recorded on the CRF in response to the following question:

Is there a reasonable possibility that the study drug caused the AE?

Yes (related) A causal relationship between the study drug and the AE is a reasonable possibility.

No (not related) A causal relationship between the study drug and the AE is not a reasonable possibility.

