9.5.4.1 Reporting of Serious Adverse Events

All SAEs, regardless of their relationship to study treatment, must be reported on a completed SAE form by email or fax as soon as possible but no later than 1 business day from the date the investigator becomes aware of the event.

SAEs, regardless of causality assessment, must be collected through the through the last visit and for 28 days after the subject's last dose. All SAEs must be followed to resolution or, if resolution is unlikely, to stabilization. Any SAE judged by the investigator to be related to the study treatment or any protocol-required procedure should be reported to the sponsor regardless of the length of time that has passed since study completion.

The detailed contact information for reporting of SAEs is provided in the Investigator Study File.

For urgent safety issues, please ensure all appropriate medical care is administered to the subject and contact the appropriate study team member listed in the Investigator Study File.

It is very important that the SAE report form be filled out as completely as possible at the time of the initial report. This includes the investigator's assessment of causality.

Any follow-up information received on SAEs should be forwarded within 1 business day of its receipt. If the follow-up information changes the investigator's assessment of causality, this should also be noted on the follow-up SAE form.

Preliminary SAE reports should be followed as soon as possible by detailed descriptions including copies of hospital case reports, autopsy reports, and other documents requested by the sponsor.

The investigator must notify his/her IRB/IEC of the occurrence of the SAE, in writing, if required by their institution. A copy of this communication must be forwarded to the sponsor to be filed in the sponsor's Trial Master File.

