9.5.4.3.2 REPORTING OF STUDY-SPECIFIC EVENTS

Study-specific events (listed below) should always be considered as serious important medical events and be entered on the Adverse Event CRF and reported using the procedures detailed in Reporting of Serious Adverse Events ([Section 9.5.4.1](#)), even if the study-specific event does not meet other serious criteria.

- Serotonin syndrome Must have at least 1 of the following: spontaneous clonus; inducible clonus plus agitation or diaphoresis; Ocular clonus plus agitation or diaphoresis; Tremor plus hyperreflexia; Hypertonia plus temperature above 38°C plus ocular clonus or inducible clonus
- Psychosis
- Suicidal behavior
- Priapism
- New onset of valvular heart disease
- New onset pulmonary hypertension
- Malignant neoplasms, with the exception of basal cell and squamous cell carcinomas of the skin
- Fibroadenomas of the breast or ductal carcinoma in situ

The following additional study specific AE of interest should be reported using the procedures detailed in Reporting of SAEs ([Section 9.5.4.1](#)), even if the study-specific event does not meet serious criteria. If the event meets seriousness criteria, it should be reported as an SAE as above. However, if the event listed below does not meet serious criteria, it should be noted as nonserious on the Adverse Event CRF:

- Suicidal ideation
- Euphoria

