9.5.5 Completion/Discontinuation of Subjects

The investigator may withdraw the subject from the study at any time for safety or administrative reasons. A subject may elect to discontinue the study at any time for any reason. All subjects will continue in the study until the 52-week evaluation is completed. Subjects who discontinue treatment prematurely will be followed up until study completion. All subjects who discontinue the study are to complete the study's early discontinuation procedures indicated in the Schedule of Procedures/Assessments ([Table 2](#)).

The investigator will promptly explain to the subject involved that the study will be discontinued for that subject and provide appropriate medical treatment and other necessary measures for the subject. A subject who has ceased to return for visits will be followed up by mail, phone, or other means to gather information such as the reason for failure to return, the status of treatment compliance, the presence or absence of AEs, and clinical courses of signs and symptoms.

Subjects who discontinue early from the study will be discontinued for 1 of these primary reasons: AE(s), lost to follow-up, subject choice, withdrawal of consent, pregnancy, study terminated by sponsor, or other. In addition to the primary reason, the subject may indicate 1 or more of secondary reasons for discontinuation. Study disposition information will be collected on the Subject Disposition CRF.

Detailed retention strategies will be developed and included in study manual. These include a highly trained and competent staff, easy access to the clinic, reminder and follow-up calls, interactive group sessions with games and hands-on nutrition and physical activity demonstrations, random raffle drawings, social events, birthday and holiday cards, and newsletters. In addition, home visits for assessments of families will be an option, as needed, to maximize data collection. This detailed retention plan will help prevent missing data.

A subject removed from the study for any reason may not be replaced.

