9.7.1.8.2 ADVERSE EVENTS

The AE verbatim descriptions (investigator terms from the CRF) will be classified into standardized medical terminology using the Medical Dictionary for Regulatory Activities (MedDRA). Adverse events will be coded to the MedDRA (Version 18.0 or higher) lower level term closest to the verbatim term. The linked MedDRA PT and primary system organ class (SOC) are also captured in the database.

A treatment-emergent AE (TEAE) is defined as an AE that emerges during treatment (up to 28 days after the last dose of study drug), having been absent at pretreatment (Baseline) or

- Reemerges during treatment (up to 28 days after the last dose of study drug), having been present at pretreatment (Baseline) but stopped before treatment, or
- Worsens in severity during treatment relative to the pretreatment state, when the AE is continuous.

Only those AEs that were treatment emergent will be included in summary tables. All AEs, treatment emergent or otherwise, will be presented in subject data listings.

The TEAEs will be summarized by treatment group. The following summaries will be reported for TEAES:

- Incidence of TEAEs in descending order of frequency
- Incidence of TEAEs by SOC and PT
- Incidence of treatment-related TEAEs by SOC and PT
- Incidence of TEAEs by SOC, PT and maximum severity (mild, moderate, or severe)
- Incidence of treatment-related TEAEs by SOC, PT, and maximum severity (mild, moderate, or severe)
- Incidence of TEAEs by SOC, PT, and relationship to study drug (Yes [related] or No [not related])

A subject will be counted only once within a SOC or PT, if the subject experienced more than 1 TEAE within a specified SOC and PT.

The following summaries will also be presented for the treatment-emergent SAEs.

- Incidence of TEAEs leading to death
- Incidence of treatment-emergent SAE by SOC and PT
- Incidence of treatment-related treatment-emergent SAE by SOC and PT

In addition, subjects with TEAEs leading to discontinuation from study drug and AEs of special interest as described in Section 9.5.4.3.2 will be summarized by MedDRA SOC and PT for each treatment group.

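### Sections 9.5.1.5.1 and 9.5.4.1 state the SAE collection window differently for subjects who stop drug early and stay in the study, and late SAEs have no by-arm summary

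*Protocol*

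**What the plan says.** All references are to the protocol text for ages 12 to 17.

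- **Collection, Section 9.5.1.5.1.** All AEs "should be collected beginning from the time the subject signs the study ICF through the last visit in the Treatment Phase". Later in the same paragraph SAEs get a sentence of their own: "SAEs will be collected for 28 days after the last dose".
- **Collection, Section 9.5.4.1.** SAEs, whatever their cause, "must be collected through the through the last visit and for 28 days after the subject's last dose" (the repeated words are in the document). SAEs judged related to treatment or to a required procedure are reportable at any later time.
- **Follow-up, Section 9.5.5.** "Subjects who discontinue treatment prematurely will be followed up until study completion". Section 9.1 says the same and keeps all subjects to the 52-week evaluation. Table 2 marks AE monitoring at every visit up to the end-of-study visit at Week 56.
- **Tabulation, Section 9.7.1.8.2.** A treatment-emergent event is one that "emerges during treatment (up to 28 days after the last dose of study drug), having been absent at pretreatment (Baseline"), with a similar limit for re-emerging events. "Only those AEs that were treatment emergent will be included in summary tables". The listed summaries of deaths and SAEs are in treatment-emergent terms. All collected AEs go into subject listings. A closing sentence adds a summary of the special-interest events of Section 9.5.4.3.2.

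**The concern.** The protocol deliberately keeps subjects under observation after they stop drug, and for exactly those subjects its two SAE rules need not agree. A site working from Section 9.5.1.5.1 may stop entering SAEs 28 days after the last dose, while a site working from Section 9.5.4.1 continues to the last visit. An event that was never collected cannot be recovered at analysis.

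The tabulation rule adds a second, smaller problem. An SAE that is collected more than 28 days after the last dose does not count in the SAE or death summaries. Unless it has a summary of its own, the report shows it only as a line in a listing, with no incidence by randomised group. Subjects who stopped because they tolerated treatment poorly are among those affected, and their later course bears on the safety question.

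**Working it through.** No stated figure is in dispute. The check compares the windows in weeks, counting 28 days as 4 weeks.

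**Inputs.** Treatment lasts 52 weeks (Section 9.1). The end-of-study visit is at Week 56 (Table 2). The post-dose window is 28 days (Sections 9.5.1.5.1, 9.5.4.1 and 9.7.1.8.2). Subjects off drug are followed to study completion (Section 9.5.5).

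**Completers.** Last dose at Week 52: 52 × 7 + 28 = 392 days, and 56 × 7 = 392 days. Both collection rules and the treatment-emergent window end at the end-of-study visit, so there is no conflict.

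**Subjects who stop drug and stay.** The 28-day window closes at week of last dose + 4. Time left to Week 52 = 52 − (week of last dose + 4), or 0 if negative.

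| Last dose (week) | 28-day window closes (week) | Weeks left to Week 52 |
|---|---|---|
| 5 | 9 | 43 |
| 12 | 16 | 36 |
| 20 | 24 | 28 |
| 28 | 32 | 20 |
| 36 | 40 | 12 |
| 44 | 48 | 4 |
| 48 | 52 | 0 |

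For a last dose at Week 12, collection after the last dose lasts 4 weeks on a literal reading of the SAE sentence in Section 9.5.1.5.1. Under Section 9.5.4.1 it lasts at least 52 − 12 = 40 weeks.

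**Scale.** The protocol does not state how many subjects will stop drug and stay. Purely as a unit of scale, ten such subjects who all stopped at Week 12 would contribute 10 × 36 / 52 ≈ 6.9 person-years before Week 52 outside the 28-day window.

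**What reaches a by-arm summary when it occurs in that time.**

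- Valvulopathy and pulmonary hypertension on echocardiography: yes. Sections 9.7.1.8 and 9.7.1.8.6 summarise them by arm at Weeks 28 and 52, with no 28-day limit.
- C-SSRS findings: yes. Section 9.7.1.8.6 summarises them by arm at each scheduled visit.
- The Section 9.5.4.3.2 events as reported AEs (for example psychosis or malignant neoplasm): unclear. The closing sentence of Section 9.7.1.8.2 refers to TEAEs leading to discontinuation but to AEs of special interest. That may mean no time limit, but the general restriction to treatment-emergent events stands earlier in the same section and is not lifted.
- Deaths, hospitalisations and other SAEs: no. They appear in listings only.

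**The case against.** The best reply is that Section 9.5.1.5.1 sets no stop. An SAE is an AE, and the same paragraph collects all AEs through the last Treatment Phase visit. The SAE sentence contains neither an only nor an until. It can be read as adding a 28-day tail, which would match Section 9.5.4.1; the opposite reading would collect a mild event at Week 30 and omit a serious one. This largely stands: the wording is ambiguous and does not expressly end collection. It does not remove the problem. The sentence does not say that it adds to anything. Treatment Phase is also not clearly defined: Section 9.1 names a Prerandomization and a Randomization Phase, and only the heading of Section 9.1.2 uses the term, over text that includes the Follow-Up Period. Sites should not have to work this out.

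A second reply is that a 28-day treatment-emergent window is ordinary practice and that extra tables belong in the SAP. That is fair, and it makes the tabulation half the lighter one. But Section 9.7.1.8.2 itself fixes which events may be tabulated, and no SAP can restore SAEs that sites did not collect.

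A reader might go further and infer that late valve disease disappears from the safety tables. A subject who stops at Week 8 and stays has the next scheduled echocardiogram at Week 28, 20 weeks after the last dose. The document does not support that inference, because the separate echocardiographic summaries have no 28-day limit. Nor are collected late events discarded: they stay in listings, and related SAEs remain reportable at any time. Finally, the 40% in Section 9.7.2 is a dropout allowance for the power calculation. It does not count subjects who stop drug and remain, so it cannot serve as the base for the number affected.

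**Conclusion.** The point holds as a conflict of wording with a limited consequence. Sections 9.5.1.5.1 and 9.5.4.1 agree for completers and can be applied differently for subjects who stop drug and stay. At a last dose in Week 12 the difference is 36 weeks to Week 52; it shrinks to nothing for a last dose at Week 48 or later. This rests on a literal reading of the SAE sentence in Section 9.5.1.5.1, which is a possible reading but not the only one.

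Separately, and on any reading, deaths, hospitalisations and other SAEs that emerge more than 28 days after the last dose have no by-arm incidence under Section 9.7.1.8.2. Whether the special-interest summary shares that limit cannot be settled from the text. The protocol gives no count of the subjects concerned, so the total effect is unknown. The correction is cheap, and the collection part has to be made while data are being gathered.

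**What to change.** 1. Reconcile Section 9.5.1.5.1 with Section 9.5.4.1 so that both state one SAE collection window: through the last study visit or 28 days after the last dose, whichever is later.
2. In Section 9.7.1.8.2, add one summary by randomised arm of all SAEs, deaths and Section 9.5.4.3.2 events from first dose to last study visit, irrespective of time since the last dose. Keep the 28-day treatment-emergent tables beside it. This also settles the doubt about the special-interest events.

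The cost is a sentence of reconciled wording and one extra table. No visits are added, since AE monitoring is already scheduled at each one. The drawback is that the whole-study table includes events off drug, which may dilute a drug effect; that is why the treatment-emergent tables should stay.
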